#### **3.2 Study Design Rationale**

This study is designed to evaluate the long-term safety and disease control in MCD subjects. Because siltuximab is an investigational agent, further evaluation is necessary to better understand the long-term safety of siltuximab in this population. Focused safety monitoring will be performed for key safety events of interest (see the current Investigator's Brochure), including infections, hyperlipidemia, neutropenia,

thrombocytopenia, GI perforations, infusion-related reactions, liver enzyme abnormalities, and immunogenicity.

### **Dose Justification**

The dose of siltuximab for this study is 11 mg/kg administered every 3 weeks by a 1-hour IV infusion. This corresponds to the 12 mg/kg dose used in C0328T03 when the current absorptivity constant is applied (see Section 4.2.1 of the Investigator Brochure). In the C0328T03 study, a dose response in MCD was seen, and was not associated with dose-related toxicity ([van Rhee et al, 2010](#)). Preliminary pharmacokinetic/pharmacodynamic modeling data is also supportive, because suppression of CRP to below the (LOQ; ie, 1 mg/L using high-sensitivity methods) throughout the treatment period does not occur with lower doses that have been tested ([Puchalski et al, 2010](#); data on file).

### **Patient-reported Outcomes**

The MCDSS will be assessed only in the subjects previously treated in the C0328T03 study, to provide an independent assessment of the scale designed for the CNTO328MCD2001 study ([Vernon et al, 2009](#)). The scale, developed based on results of qualitative research with MCD patients and clinical experts, was subsequently field tested with additional MCD patients. Symptom presence/absence and severity are noted on an anchor-based numeric scale. Frequency of occurrence can be generated when the instrument is used as a daily record of symptoms, as the recall period is 24 hours. Completion time is approximately 5 minutes. A summary score is generated based on the scores of 0 (very mild) to 5 (very severe). See Section 9.3.4 for additional information.

### **Pharmacodynamic Biomarker Assessments**

In order to gain further insight into the role of IL-6 in MCD, quantification of IL-6 will be performed and assessment of unusual IL-6 splice variants may also be performed to determine their role in MCD manifestation and response to treatment. The information from these evaluations may contribute to understanding IL-6 biology and siltuximab efficacy in MCD and in predicting or explaining treatment resistance over time. Collection of samples for these assessments will be stopped after Amendment INT-4 is implemented. Assessments are described in Section 9.4 and the planned analyses are described in Section 11.6.

### **Immunogenicity Assessment**

An immunogenic response to siltuximab is possible; therefore, samples to determine the presence of antibodies to siltuximab are planned to be collected from all subjects in the study. The information from these samples and data from other studies will be used to determine the immunogenicity of siltuximab in this population. Assessments are described in Section 9.6.

## Glycoform Clearance Analysis and In Vivo Protein Degradation

Blood samples will be collected from subjects to study the clearance and degradation of siltuximab glycoforms at several timepoints during Cycle 1 (see Section 9.5). Siltuximab contains several different chemical structures due to small differences in glycosylation. Serum collected from these blood samples will be analyzed to determine if there are differences in the clearance of the different glycoforms which could impact clinical efficacy. Changes in the chemical structure of siltuximab will also be monitored after product administration to determine the circulating levels of different protein degradants. Together, this information will be used to refine acceptance specifications for product release and stability.

## 4 STUDY POPULATION

### 4.1 General Considerations

The inclusion and exclusion criteria for enrolling subjects in this study are described in the following sections. No deviations from these criteria are allowed. **NOTE:** Investigators must ensure that all inclusion and exclusion criteria have been met at screening. Re-screening of screening failures is allowed. A subject is considered eligible if the last observation prior to the first dose meets the inclusion and exclusion criteria.

### 4.2 Inclusion Criteria

Potential subjects must satisfy all of the following criteria to be enrolled in the study:

1. Subjects must have multicentric Castleman's disease.
2. Subjects must have previously been enrolled in study C0328T03 or CNTO328MCD2001 (either treatment arm).
3. Subjects must have had their last administration of study treatment (siltuximab or placebo) less than 6 weeks (window of plus 2 weeks) prior to first dose. Subjects with longer treatment durations since the last study treatment may be allowed after discussion with the medical monitor.
4. Subjects must not have had disease progression while receiving siltuximab. For those subjects originally assigned to placebo in the CNTO328MCD2001 study, subjects who have received less than 4 months of siltuximab following crossover will also be eligible.
5. Adequate clinical laboratory parameters within 2 weeks prior to the first dose of siltuximab for this protocol:
  - a. Absolute neutrophil count (ANC) greater than or equal to  $1.0 \times 10^9/L$  ( $1,000/mm^3$ ) with or without neutrophil growth factors

- b. Platelets greater than or equal to  $50 \times 10^9/L$  ( $50,000/mm^3$ ) with or without platelet transfusion, thrombopoietic cytokines, or both
  - c. AST, ALT, total bilirubin and alkaline phosphatase must be within 2.5 x ULN; if alkaline phosphatase is above that, at least alkaline phosphatase liver fraction has to be less than or equal to 2.5 x ULN
6. Any other clinical significant toxicity must be less or equal to Grade 2 or the baseline value of the previous study.
  - 7.1 Women of childbearing potential must agree to use adequate birth control measures during the study and for 3 months after receiving the last dose of study agent, and must have a negative pregnancy test (serum or urine beta-human chorionic gonadotropin [ $\beta$ -HCG]) at screening. Men must agree to use a double barrier method of birth control and to not donate sperm during the study and for 3 months after receiving the last dose of study agent.
  8. Sign an informed consent document indicating that they understand the purpose of and procedures required for the study and are willing to participate in the study.

### 4.3 Exclusion Criteria

Potential subjects who meet any of the following criteria will be excluded from participating in the study:

1. Unmanageable toxicity, an adverse event, progression of disease, or withdrawal of consent as reason for discontinuing treatment from previous sponsor-initiated siltuximab study.
2. Vaccination with live, attenuated vaccines within 4 weeks of first dose of this study.
3. Criterion removed per amendment INT-2 (see protocol amendment table before Synopsis).
4. Known unmanageable allergies, hypersensitivity, or intolerance to monoclonal antibodies or to murine, chimeric, or human proteins or their excipients.

## 5 TREATMENT ALLOCATION

This study is an open-label, single-arm study.

## 6 DOSAGE AND ADMINISTRATION

Siltuximab will be given as a 1-hour infusion at 11 mg/kg every 3 weeks. All subjects will be treated until they progress, withdraw, experience unacceptable toxicity, or until the 6-year data cutoff, whichever comes first. A data cutoff will occur approximately 6 years after the start of enrollment; however, continued drug supply will be ensured for study subjects who would not otherwise have access to siltuximab.

Subjects with confirmed partial or complete remission, defined as a documented radiographic response, for more than 6 months (including those entering the study in PR or CR) may be dosed every 6 weeks at the investigator's discretion. Demonstration of radiographic response is not required for subjects with skin-only disease with confirmed PR/CR for more than 6 months. Subjects on the 6-week schedule should be monitored for safety and disease assessment evaluations as per protocol Time & Events Schedules (see [Table 1](#) and [Table 2](#)). When disease progression is suspected, all screening and pre-dose Cycle 1 evaluations should be repeated and treatment with siltuximab could continue at 11 mg/kg siltuximab every 3 weeks. The effective switch from the 3-week dosing schedule to the 6-week schedule can only occur on odd-numbered cycle visits to match the collection timepoints of biomarkers and immunogenicity samples of every 12 weeks, and has to occur on dosing days. Switching back to a 3-week schedule upon suspected disease progression can occur at any cycle visit.

During the study, no dose modifications of siltuximab will be allowed. Dose delays of up to 3 weeks will be allowed for treatment-related toxicity. Documentation of dose delays, including the reasons for the delay, is required.

## **6.1 Dose Delays and Retreatment**

The dose should be delayed if the subject has an active infection that qualifies for a Grade 3 or 4 NCI-CTCAE toxicity, or that is otherwise considered clinically significant by the investigator.

### **6.1.1 Laboratory Assessment and Dose Delays**

Chemistry and hematology laboratory tests are performed every 3 administration visits for subjects on the 3-week dosing schedule and on siltuximab at study entry. If the dosing schedule exceeds the 3-week interval (eg, every 6 weeks), these laboratory assessments should be performed every other administration visit at a minimum, to ensure proper safety evaluation. For subjects who are naïve to siltuximab at study entry, chemistry and hematology laboratory tests are performed at every administration visit for the first year on study. Lipid panels are monitored approximately every 6 months, and every 3 months for siltuximab-naïve subjects.

The siltuximab dose must be delayed if the hemoglobin value measured predose is  $\geq 17$  g/dL, as a safety precaution to avoid clinical consequences of polycythemia.

More frequent laboratory assessment as described above is not required; however, the investigator should consider delaying treatment when laboratory values do not meet those required for inclusion in the study.

## **6.2 Guidelines for Management of Infusion Reactions**

Although unlikely, serious allergic reactions (including anaphylaxis) may occur at any time during the administration of monoclonal antibodies, including siltuximab. Therefore,

before any administration is started, the appropriate personnel, medication (adrenaline, inhaled beta agonists, antihistamines, and possibly corticosteroids) and other requirements to treat anaphylaxis must be available.

A physician must also be immediately available at the site at all times during the administration of study agents. The Medical Monitor must be notified within 24 hours of any infusion reaction requiring interruption of study agent (see Contact Information pages provided separately). Subjects experiencing a reaction during the administration of study agent should be treated according to institutional guidelines.

All subjects should be observed carefully for infusion-site reactions (eg, erythema or induration), symptoms of an allergic reaction/hypersensitivity (eg, urticaria, itching, hives), or cytokine release syndrome/acute infusion reaction. Any adverse reaction should be noted on the AE page of the CRF. The infusion rate may be lowered if clinically indicated.

Infusion must be stopped immediately and permanently discontinued if:

- $\geq$  Grade 3 allergic reaction/hypersensitivity (including drug fever) occurs
- $\geq$  Grade 3 cytokine release syndrome/acute infusion reaction occurs

Subjects with reactions, during or after an infusion, resulting in bronchospasm with wheezing, dyspnea requiring ventilatory support, or symptomatic hypotension with a decrease in systolic blood pressure greater than 40 mm Hg will not be permitted to receive any additional study agent for the remainder of the study. If the infusion reaction results in treatment discontinuation, subjects should undergo all scheduled study evaluations.

Corticosteroid use for allergic reactions to siltuximab should be limited to 2 doses of 100 mg hydrocortisone or equivalent (see [Attachment 1](#)), in addition to standard treatment with antihistamines and acetaminophen (see Section [8.2](#)).

A blood sample should be obtained, if possible, for determining antibodies to siltuximab any time an infusion reaction is observed or reported during the study. Siltuximab serum concentration will also be determined from the sample for the purpose of interpreting data on antibodies to siltuximab. These samples will be stored, and evaluated if deemed necessary.

## 7 TREATMENT COMPLIANCE

Study drug will be administered as an IV infusion by qualified staff and the details of each administration will be recorded in the CRF (including date, start and stop times of the IV infusion, total volume given if administration was stopped early).

## 8 CONCOMITANT THERAPY

Prestudy therapies administered up to 30 days before first dose of study drug in this study must be recorded at screening. Concomitant medications must be recorded throughout the study beginning when the first dose of study drug is administered until 30 days after last dose. All concomitant medications will be collected except for:

- Vitamins
- Herbal medicines
- Dietary supplements (iron is not considered a dietary supplement)

After Amendment INT-4 is implemented, only the following concomitant medications will continue to be collected:

- Anti-infective medications (antibiotics, oral or topical antifungals, and antiviral etc.)
- Lipid modifying agents
- Antihypertensives
- Immunomodulators including corticosteroids
- Hematopoietic cytokines such as colony stimulation factors
- Blood product transfusions
- Clinical important surgery or procedures
- Medications to manage infusion related reactions
- Medications used to treat SAEs

### 8.1 Supportive Care Measures

Allowed supportive care measures for all study subjects to manage symptoms include:

- Management of effusions (eg, drainage, diuretics)
- Antipyretics, antipruritics, antihistamines
- Pain medication
- Management of infections
- Transfusions
- Management of infusion reactions as specified in institutional guidelines (see Section 6.2)

## 8.2 Guidelines for Corticosteroid Use

Concomitant use of immunosuppressive therapy is not permitted during the study, except for:

- Subjects who are receiving corticosteroid treatment at the time of screening may be considered for inclusion in the study. If subjects are taking corticosteroids at the start of the study, they may be tapered during the study. Tapering of corticosteroid dosing should preferably not start before the first disease assessment (ie, Cycle 4). Tapering of corticosteroids should be guided by clinical symptoms of Castleman's disease unless prompted by intolerable or acute and severe corticosteroid-related toxicities.
- Other indications, see Section 8.4
- Treatment of acute allergic reactions according to institution guidelines (see Section 6.2)
- Secondary prophylactic pretreatment with corticosteroids to prevent allergic reactions (eg, to contrast materials or to siltuximab) is allowed after consulting with the Medical Monitor. Corticosteroid use for allergic reactions to siltuximab should be limited to 2 doses of 100 mg hydrocortisone or equivalent (see Attachment 1), in addition to standard treatment with antihistamines and acetaminophen (see Section 6.2).

## 8.3 Guidelines to Manage Hyperlipidemia

Hypertriglyceridemia has been observed in some subjects who were administered siltuximab and has been seen with other agents targeting the IL-6 receptor ([Actemra® PI, 2010](#); [RoActemra EPAR, 2009](#); [Nishimoto et al, 2004](#)). The incidence of hypertriglyceridemia reported as an AE in single-agent studies of siltuximab is low and almost all reported events have been low grade. Monitoring and treatment of lipid profiles (high-density lipoprotein [HDL] and low density lipoprotein [LDL]) and triglycerides as per established guidelines (<http://www.nhlbi.nih.gov/guidelines/cholesterol/dskref.htm>) are recommended since potential effects of chronic siltuximab administration on cardiovascular ischemic events is not well defined.

## 8.4 Prohibited Therapies

Use of these prohibited treatments during the study will result in subjects being withdrawn from the study:

- Other concomitant antitumor therapies for Castleman's disease, for example:
  - Anti-CD20 antibodies (eg, rituximab)
  - IL-6 targeted therapies (eg, tocilizumab)
  - Cytotoxic chemotherapy
- Biologic treatments such as tumor necrosis factor alpha (anti-TNF $\alpha$ ) antibodies (eg, infliximab, adalimumab, etanercept)

- Other investigational agents
- Increase from baseline or a new course of systemic immunosuppressive agents (including corticosteroids), with the exception of:
  - isolated use of low-dose corticosteroids to treat and prevent allergic reactions (see Section 8.2)
  - increase or new course for another indication such as but not limited to (a flare of) rheumatoid arthritis and psoriasis
- ESAs

The Medical Monitor must be notified in advance (or as soon as possible thereafter) of any instances in which prohibited therapies are administered.

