### **3 OVERVIEW OF STUDY DESIGN**

#### **3.1 Study Design**

This is an open-label, multicenter, non-randomized Phase 2 study of the safety of extended treatment with siltuximab in subjects who were previously enrolled in siltuximab studies of MCD (C0328T03 and CNTO328MCD2001). Up to 75 subjects will be eligible for the study, the majority of whom will be on active therapy with siltuximab at the time of enrollment. Duration of disease control and survival will also be assessed. Other secondary objectives include quantification of IL-6 (see Section 9.4) and assessment of the reliability of the MCDSS (see Section 9.3.4).

Subjects must be either siltuximab-naive or have not progressed on siltuximab in the opinion of the investigator. All subjects will be treated until they progress, withdraw, experience unacceptable toxicity, or until the 6-year data cutoff, whichever comes first.

Two data cutoffs will occur:

- No later than 2 years after the start of enrollment, an interim analysis will be conducted to further evaluate the benefit and safety of long-term treatment with siltuximab in subjects with MCD.
- Approximately 6 years after start of enrollment; however, continued drug supply will be ensured for study subjects who would not otherwise have access to siltuximab. A clinical study report (CSR) will be written based on this data cutoff.

Data collection for subjects who discontinue study agent will be limited to survival status, occurrence of malignancies, and subsequent therapies for MCD, which will be assessed twice per year until the subject has been lost to follow-up or has withdrawn consent for the study, or the 6-year data cutoff; whichever occurs first. For subjects still on treatment provided by Sponsor after the 6-year data cutoff, pregnancies and SAEs, including information on study agent administration and concomitant medications associated with an SAE, will continue to be collected. Data collected beyond the 6-year data cutoff will be reported to the appropriate health authorities in safety update reports. The end of study is the date of the last assessment for the last subject.

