#### **9.3.3 Survival**

For subjects who discontinue study agent, survival status will be assessed twice per year until the subject has been lost to follow-up or has withdrawn consent for the study, or the 6-year data cutoff; whichever occurs first.

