### 10.2 Discontinuation of Treatment

All subjects will be treated until they progress, withdraw, experience unacceptable toxicity, or until the 6-year data cutoff, whichever comes first. A data cutoff will occur

approximately 6 years after the start of enrollment; however, continued drug supply will be ensured for study subjects who would not otherwise have access to siltuximab outside this clinical study.

If a subject discontinues study agent, obtain end-of-treatment and follow-up assessments, which are the same assessments done at Follow-up Weeks 4, 8 and 12 as applicable. If a subject's study treatment must be discontinued before the end of the treatment regimen, this will not result in automatic withdrawal of the subject from the study. Subjects will have follow-up assessments for survival, occurrence of malignancies, and subsequent MCD therapies until the 6-year data cutoff (see Section 9.3.3).

A subject's study treatment should be discontinued if:

- The investigator believes that for safety reasons (eg, adverse event) it is in the best interest of the subject to stop treatment.
- The subject becomes pregnant.
- The subject initiated any of the prohibited medications requiring discontinuation of treatment (see Section 8.4)

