### 10.3 Withdrawal from Study

A subject will be withdrawn from the study for any of the following reasons:

- Lost to follow-up
- Withdrawal of consent
- Death

If a subject discontinues the study before the end of the treatment phase, obtain end-of-treatment and follow-up assessments.

In case a subject is lost to follow-up, every possible effort must be made by the study site personnel to contact the subject and determine the reason for discontinuation/withdrawal. The measures taken to follow up must be documented.

When a subject withdraws before completing the study, the reason for withdrawal is to be documented in the CRF and in the source document. Subjects who withdraw will not be replaced.

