4.7. Subsequent MCD Therapy

The total number of subjects who received subsequent MCD therapy will be reported. A summary of subsequent anticancer therapy will be presented by therapeutic class, pharmacologic class and drug name.

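### Protocol 8.4 withdraws users of prohibited therapy from the study, while 10.2 stops only their treatment and continues follow-up; the two must be reconciled

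*Protocol*

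**What the plan says.** Protocol 8.4 opens its list of prohibited therapies with the consequence of using one: "Use of these prohibited treatments during the study will result in subjects being withdrawn from the study". The list covers other concomitant antitumor therapy for Castleman's disease (anti-CD20, IL-6 targeted and cytotoxic agents), biologics such as anti-TNF agents, other investigational agents, new or increased systemic immunosuppression with stated exceptions, and erythropoiesis-stimulating agents.

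Protocol 10.2 deals with the same event differently. Among the reasons for stopping study treatment it lists "The subject initiated any of the prohibited medications requiring discontinuation of treatment (see Section 8.4"). Of a subject whose treatment stops early it says "this will not result in automatic withdrawal of the subject from the study", and it goes on: "Subjects will have follow-up assessments for survival, occurrence of malignancies, and subsequent MCD therapies until the 6-year data cutoff".

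Protocol 10.3 begins "A subject will be withdrawn from the study for any of the following reasons" and names three: loss to follow-up, withdrawal of consent and death. Protocol 3.1 continues off-treatment data collection "until the subject has been lost to follow-up or has withdrawn consent for the study, or the 6-year data cutoff". Protocol 9.3.3 has the same end points for survival status, and SAP 1.1 repeats the rule in 3.1.

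The SAP relies on these data. On subsequent therapy, SAP 4.7 states "The total number of subjects who received subsequent MCD therapy will be reported". SAP 5.2.4 plans a Kaplan-Meier analysis of overall survival with rates at 3, 4, 5 and 6 years.

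**The concern.** The protocol distinguishes leaving treatment from leaving the study, and the distinction decides what is collected. A subject off treatment is contacted twice a year for survival, malignancies and subsequent therapy. A subject withdrawn from the study has no such schedule. Section 8.4 places users of listed therapies in the second group and 10.2 places them in the first, so two sites could each follow the protocol and collect different data on the same kind of subject.

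The effect reaches safety reporting. Under 12.2.1, a subject who receives further MCD treatment within the 30-day reporting window still has related adverse events reported, except where that subject has been withdrawn from the study. A literal reading of 8.4 triggers that exception, and long-term safety is the primary objective.

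For overall survival, the question is whether subjects whose follow-up ends this way have the same risk of death as those who stay. If their risk is higher, censoring is informative and the Kaplan-Meier estimate is too high.

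**Working it through.** **Comparison of the text**

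| Place | Consequence for a subject who uses a listed therapy |
|---|---|
| Protocol 8.4 | Withdrawn from the study |
| Protocol 10.2 | Study treatment stopped; no automatic study withdrawal; follow-up to the 6-year cutoff |
| Protocol 10.3 | Not among the three withdrawal reasons |
| Protocol 3.1, SAP 1.1 | Not a reason to end follow-up |
| Protocol 9.3.3 | Not a reason to end survival contacts |
| Protocol 12.2.1 | Related adverse events reported in the 30-day window unless withdrawn from the study |
| Protocol 11.4.3, SAP 5.2.4.1 | Not a named censoring reason; no rule for a withdrawal imposed under 8.4 |

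No section says that the wording of 8.4 means withdrawal from treatment only. The conflict is in the current text. The amendment log suggests a cause: INT-2 added follow-up for survival and subsequent therapy, INT-3 added malignancies, and neither lists 8.4 among the sections changed for that purpose. That cause is an inference.

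**Illustration of the survival bias**

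The plan has no figure to reproduce. It gives neither the share of subjects who would start a listed therapy nor their mortality, so every input here is an assumption:

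- share starting: p = 10%, 20% or 30%, with start times uniform over 6 years
- death hazard before starting: 0.02/year
- death hazard after starting: h = 0.02 (no change), 0.05, 0.10 or 0.20/year
- all starters lost at the moment they start

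Kaplan-Meier with censoring at the start sees only the earlier hazard: S_KM(6) = exp(−0.02 × 6) = 88.7%.

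For starters, true survival is that figure times f = (1 − exp(−d))/d, where d = 6(h − 0.02), with f = 1 when d = 0. Overall, S_true(6) = 88.7% × [(1 − p) + p·f], so the bias is 88.7% × p × (1 − f).

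| h per year | d | f | Bias, p = 10% | p = 20% | p = 30% |
|---|---|---|---|---|---|
| 0.02 | 0 | 1 | 0 | 0 | 0 |
| 0.05 | 0.18 | 0.915 | 0.8 | 1.5 | 2.3 |
| 0.10 | 0.48 | 0.794 | 1.8 | 3.7 | 5.5 |
| 0.20 | 1.08 | 0.611 | 3.4 | 6.9 | 10.3 |

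Bias is in percentage points. In the worst cell, true 6-year survival is 78.4% against an estimate of 88.7%.

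Partial loss shrinks these figures. If half the starters stay in follow-up, the hazard that Kaplan-Meier estimates at time t is (0.02·A + h·B)/(A + B). Here A = exp(−0.02t)(1 − pt/6) counts those who have not started, and B = ½(p/6)·exp(−0.02t)·[1 − exp(−(h − 0.02)t)]/(h − 0.02) counts the retained starters. Integrated numerically over 6 years, the worst cell falls from 10.3 to 4.6 points. With no loss the bias is zero.

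For scale, with 75 subjects the binomial standard error of an 89% survival rate is √(0.89 × 0.11/75) = 3.6 points. Start rates of 10–30% would mean about 8 to 22 people.

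**The case against.** The strongest reply is that the protocol already shows which reading is meant. Section 10.2 cites 8.4 by number and describes the therapies as ones that require treatment to stop. Section 10.3 reads as a closed list, and 3.1, 9.3.3 and SAP 1.1 all leave prohibited therapy out of the reasons to end follow-up. Section 12.2.1 expects some subjects on further MCD therapy to remain in the study. One sentence stands against all of these. This is fair, and it is why the loss is possible rather than certain. But 8.4 is the section a site consults when a prohibited drug is given, and its instruction is explicit.

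The scope is also limited. A reader might infer that the 8.4 list is the same set of therapies that SAP 4.7 counts. The documents do not support that. Section 8.4 belongs to the concomitant-therapy section, and its antitumor item concerns therapy given alongside siltuximab. Progression at two consecutive assessments already ends treatment under 9.3.1, and therapy started after that is subsequent rather than concomitant. The phrase about use during the study leaves some ambiguity, but the exposed group is mainly subjects who start a listed agent while still on siltuximab.

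The loss is cushioned as well. Section 8.4 requires the Medical Monitor to be told of the therapy, so the SAP 4.7 count need not miss it; later lines are more at risk. Consent under 16.2.3 allows recontact for survival status. Section 10.3 asks for end-of-treatment and follow-up assessments when a subject leaves the study early. None of these replaces twice-yearly contact to the cutoff.

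A reader might also infer that the affected subjects are those doing worst. That is plausible for new antitumor therapy or steroid escalation and weaker for anti-TNF agents or other investigational drugs. The documents do not state it, and 8.4 exempts immunosuppression for allergic reactions and for other indications.

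**Conclusion.** The inconsistency is real and needs correcting: 8.4 cannot be followed to the letter together with 10.2 on whether the subject stays in the study. Section 10.3 supports 10.2 only by omission. It does not order follow-up; that duty is in 10.2, 3.1 and 9.3.3.

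The possible consequence is loss of survival, malignancy and later subsequent-therapy data, and of related adverse event reports within the 30-day window, at sites that apply 8.4 literally.

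It would be tempting to quote a survival bias of 2 to 10 points as the finding, but the documents do not support that. The arithmetic holds only under assumed start rates, an assumed five- to tenfold rise in the death hazard and loss of every starter. Over the wider set of assumptions the bias runs from nil, through about 1–2 points at 0.05/year after starting, to about 10 points at 0.20/year with 30% starting, and less with partial loss. The low end lies within sampling error for 75 subjects. The illustration also uses a plain 6-year clock, whereas SAP 5.2.4.1 measures survival from first siltuximab or placebo treatment, which for most subjects precedes extension entry. Overall survival is a descriptive secondary outcome with no hypothesis test.

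**What to change.** Reword the lead sentence of protocol 8.4 so that it agrees with 10.2, 10.3, 3.1 and 9.3.3 on study status. It should cross-refer to 10.2 and state that use of a listed therapy does not by itself end follow-up for survival, malignancies and subsequent MCD therapies, which continues twice a year to the 6-year cutoff unless the subject withdraws consent or is lost to follow-up. With study status settled in this way, the exception in 12.2.1 would no longer be triggered by prohibited therapy alone.

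Optionally, add a sentence to SAP 5.2.4 confirming that starting another therapy is not a censoring reason for overall survival. This is close to redundant, because neither protocol 11.4.3 nor SAP 5.2.4.1 lists it as one, but it prevents ad hoc handling.

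The cost is one sentence in the protocol and at most one in the SAP. The follow-up contacts are already scheduled. The list of prohibited therapies and the rule for stopping treatment are not touched.
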